5.3 Inferential Statistic answering the objectives

Operational Definitions

1. Rustogi Modified Navy Plaque Index(RMNPI):

This index divides buccal and lingual surfaces into nine areas (A to I) that are scored for the presence (score=1) or absence (score=0) of plaque.

Whole mouth=Areas A,B,C,D,E,F,G,H and I; Marginal areas A,B and C; Interdental D and F

Presence of plaque: Score 1

Absence of plaque: Score 0

Buccal surface- 9 areas (A to I)

Lingual surface- 9 areas (A to I)

Interdental - D and F

RMNPI Score= $(\text{Sum of all "1" marks}) / (\text{Total number of sites score})$

2. BPI-Bleeding point index (bleeding point index, BPI; Lenox et al, 1973)

Bleeding on probing is recorded and provides evaluation of gingival inflammation around each tooth in patient's mouth

Evaluates level of oral hygiene performance

- A periodontal probe is inserted 1 mm into the sulcus at the buccal, lingual,

mesial and distal surfaces

- After 20–30s scores will be recorded
- 0 – No bleeding
- 1 – Bleeding present

Percentage of BPI = $(\text{Number of bleeding surface})/(\text{total number of dental surfaces}) \times 100$

The percentage of the number of bleeding surfaces will be calculated by:

$$\frac{\text{Number of bleeding surface}}{\text{total number of dental surfaces}} \times 100$$

Gingivitis- Inflamed gum tissue around their teeth, caused by bacteria found in dental plaque.² main types of gingivitis generalized and localized. Generalized has marginal gingivitis and diffuse gingivitis. Localized has marginal gingivitis, diffuse gingivitis and papillary gingivitis.

Dental plaque-Resilient clear to yellow-greyish substances. Primarily composed of bacteria in a matrix of salivary glycoproteins and extracellular polysaccharides .Considered to be a biofilm. Impossible to remove by rinsing or using sprays.

List of abbreviation

FB-Flossing and brushing

BF-Brushing and flossing

BPI-Bleeding Point Index

RMNPI-Rustogi modified navy plaque index

DJ- [name]

SA- [name]

JG- [name]

DHE-Dental Health Education

MMMC- Melaka-Manipal Medical College.

Chapter 1: Introduction

Dental plaque removal is critical for preventing and treating periodontal disease. Toothbrush and toothpaste are the most reliable means of plaque control. Cleaning should be thorough and performed at regular intervals. Toothbrush has limited ability to reach interdental areas. Interdental areas are prone for plaque accumulation and gingival inflammation. Regular interdental cleaning results in less gingivitis. Most effective tool has been reported to be dental floss.

1.1 Research Background

Periodontal disease is the disease of the supporting dental tissues and the most common form is plaque-induced gingivitis.¹

The removal of dental plaque is the most crucial action for preventing and treating periodontal disease.² Mechanical methods for plaque removal along with oral hygiene instructions are regarded as the first step in periodontal treatment. Toothbrush along with toothpaste are still the most reliable means of plaque control, provided cleaning is thorough and performed at regular intervals.²

Dentifrice is used as an adjunct to tooth brushing. The indication of use of dentifrices is mainly based on the presence of fluoride, antimicrobial agents that aim at further reducing the plaque formation or removal of previously established plaque. They have been used as plaque removal aids, especially because of their abrasive agents. In addition to fluoride and presence of antimicrobial agents, the actual adjunct role of dentifrices to mechanical removal of dental plaque is contradictory.²

Toothbrush has a limited ability to reach interdental areas. These areas are prone for plaque accumulation and gingival inflammation. Regular cleaning can reduce inflammation. Various products have been designed for accessing these sites such as dental flosses, interdental brushes and wooden dental sticks.² The most effective tool has been reported to be dental floss. It is effective in type 1 embrasure form. According to studies, the sequence of using toothbrush and dental floss may influence the removal of dental plaque and consequently reducing the bleeding on probing. Bleeding is one of the objective signs of periodontal disease. Therefore, it is possible

that the sequence of using a toothbrush and dental floss may influence the removal of dental plaque and consequently the BPI.¹

1.1. Problem Statements

Regular oral hygiene using toothbrush and toothpaste are the most reliable for dental plaque control. But the cleaning should be thorough and performed at regular intervals. The reason why the plaque control is most often inadequate is due to limited ability of the toothbrush to reach interdental areas which are more prone for plaque accumulation and inflammation.¹

According to a systematic review, flossing in addition to toothbrushing is better to reduce gingivitis compared to only tooth brushing. It is possible that while using the tooth brush and dental floss, the sequence of using toothbrush and dental floss may influence removal of dental plaque and gingival bleeding. Recent study by Mazhari et al in a plaque regrowth model has shown that flossing first is better than brushing first and then flossing. This has given rise to the conflict whether brushing first and then flossing is better or flossing first and then brushing is better. (reference)

1.2. Research Justification

Mechanical plaque removal has been directly related to prevention and treatment of periodontal disease. Interdental areas are the sites where plaque and inflammation are most pronounced. Dental floss is an effective tool to access these sites. Bleeding on probing is a sign of local inflammatory response related to destructive periodontitis. Tooth brushing and flossing significantly reduces gingivitis.¹ It is possible that the sequence of using toothbrush and dental floss may influence the removal of dental plaque and consequently the gingival bleeding. A study done using plaque regrowth model has reported that flossing first and then brushing is more effective. But, plaque regrowth model does not necessarily replicate the clinical situation. Cross-over clinical trials of at least two weeks duration in each phase not lasting less than two weeks with a wash out period of seven days (7 days) does provide more credible evidence. (put torkzaban article as reference). There are very few studies addressing this issue. No studies have been done among Malaysian population. Hence, this is be the first study assessing the effectiveness of sequence of flossing and brushing on gingival inflammation among dental students of MMMC..

1.3. Research Objectives

1.3.1 General Objective

To study the effectiveness of brushing and flossing sequence on plaque control and gingival inflammation

1.3.2 Specific Objectives

- a) To evaluate the effectiveness of brushing first and flossing later sequence on plaque control
- b) To evaluate the effectiveness of brushing first and flossing later sequence on gingival bleeding
- c) To evaluate the effectiveness of Flossing first and brushing later sequence on plaque control
- d) To evaluate the effectiveness of Flossing first and brushing later sequence on gingival bleeding
- e) To compare the effectiveness of Brushing first and flossing later versus Flossing first brushing later

1.4. Research Questions

- a) What is the effectiveness of brushing first and flossing later sequence on plaque control?
- b) What is the effectiveness of brushing first and flossing later sequence on gingival bleeding?
- c) What is the effectiveness of flossing first and brushing later sequence on plaque control?
- d) What is the effectiveness of flossing first and brushing later sequence on gingival bleeding?
- e) Which is better brushing first and flossing later or flossing first and brushing later?

1.5. Research Hypothesis (Null hypothesis)

The sequence of brushing and flossing doesnot influence plaque control and gingival inflammation.

Chapter 2: Literature Review

[figure not shown]
Author, Journal, Year	Material and methods	Conclusion
Mazhari F et al, J Periodontol. 2018	
 • Randomized, controlled, crossover, clinical trial • 25 Iranian dental students • Baseline - oral prophylaxis • Model - Plaque regrowth model • Phases - 2 • Phase 1- brush –floss group • Phase 2 – floss-brush group • Index - RMNPI • Wash out period- 2 weeks 	The result shows – Flossing first brushing later was better than brushing first flossing later to remove interdental plaque

Author, Journal, Year	Material and methods	Conclusion
Torkzaban P et al, Oral Health Prev Dent 13. 2015	
 • Crossover design • 35 Iranian dental students • 2 phases • Phase 1 – flossing then brushing • Phase 2 – brushing then flossing • Index- PCR and PI • Washout period- one week 	The results show – Flossing followed by brushing provides more statistically significant improvements over brushing followed by flossing with respect to plaque control

Author, Journal, Year	Material and methods	Conclusion
Worthington HV et al, Cochrane Database Syst Rev. 2019	
 Databases searched: Cochrane Oral Health's Trials Register, the Cochrane Central Register of Controlled Trials (CENTRAL) (the Cochrane Library, MEDLINE Ovid Embase and CINAHL EBSCO 	Using floss in addition to tooth brushing may reduce gingivitis or plaque, or both, more than tooth brushing alone.

Author, Journal, Year	Material and methods	Conclusion
Bagramian RA et al, American Journal of Dentistry, 2009	
 The review was compilation of major epidemiological survey of 20 different countries Assessed the prevalence of dental caries and periodontal disease 	Flossing along with regular tooth brushing is beneficial in decreasing gingival inflammation. No mention of sequence was made.

Chapter 3: Theoretical Framework/Conceptual Framework

Chapter 4: Methodology

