4.4 Variables and Research Tools

Independent Variable: Sequence of brushing and flossing

Dependent Variable: Rustogi Modified Navy Plaque Index (RMNPI) scores and bleeding point index (BPI) Scores

Tools: Head cap, Face mask, Gloves, Mouth mirror, Oral prophylaxis paste, Oral prophylaxis cup/brush, Micromotor, Disclosing agent, William's probe.

Inter examiner reliability

Prior to the start of the study, the examiner was trained by an experienced periodontist until reaching informal agreement on the diagnostic criteria. After that, calibration with 10 participants was performed. Two assessments of the scoring criteria of the index was performed with 1-hour interval. When the strength of the kappa coefficient was 0.78, the data was recorded.

Experimental procedure

Clinical Trial was registered in ClinicalTrials.gov PRS on July 4th 2019 (ID: NCT03989427). Following selection of participants after applying inclusion and exclusion criteria, written informed consent was obtained. Participants received instructions about oral hygiene from DJ. They were subjected to a thorough dental prophylaxis for complete removal of dental plaque from JG. Then, dental plaque was stained with disclosing agent followed by a mouth rinsing with water for 1 min. All erupted teeth, except for third molars, were examined by a blind examiner (SA) at 6 sites per tooth (mesio-buccal, mid-buccal, distobuccal, mesio-lingual, mid-lingual, and distolingual surfaces) for RMNPI score and BPI score.

To ensure standardization, the participants were briefed on the type of toothbrush, toothpaste and dental floss to be used in the study. The amount of dentifrice used was equivalent to half-length of the toothbrush's head. Additionally, the Bass method of brushing and Spool method of flossing was taught to the participants during the baseline appointment. . The methods of toothbrushing and flossing were explained to the participants by a step-by-step video. The participants were instructed to brush for two minutes which corresponds to 1 min for each hemiarch, 30s for buccal surfaces and 30 s for lingual/palatine surfaces.

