4.5 Statistical Analysis

We used Microsoft Excel for data entry and SPSS version 18 was used for data analysis. We calculated change score (Post – Pre) for outcome variables such as BPI scores and RMNPI scores. Descriptive statistics such as mean and standard deviation were calculated the outcome variables.

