### **Variables and Research Tools-**

**Independent variables:** age , sex, ethnicity, Academic year , Treatment order

**Dependent variables are :** BPI scores and RMNPI scores.

**Research tools:** We will be using Microsoft Excel for data entry and SPSS version 18 for data analysis. We will calculate change score (Post – Pre) for outcome variables like BPI and RMNPI scores. Descriptive statistics such as mean and standard deviation were calculated the outcome variables

[figure not shown]

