**Three-way mixed ANOVA**

To determine the effect of "Intervention" on "BPI score " is said to be moderated by "order (BF-FB or FB-BF)" and "academic year" combined.

Table 2.1: Interaction between intervention, academic year and order of intervention on BPI score

Interaction	P value
Intervention*Academic year*Order of intervention	0.061
Intervention*Academic year	0.064
Intervention*Order of intervention	0.127
Academic year*Order of intervention	0.938

Table 2.2: BPI change score (Post – Pre) between two Brushing Flossing and Flossing Brushing

	Mean (SE)	Mean difference (95% CI)	P value
Brushing Flossing	0.396 (0.410)	1.424 (0.221, 2.628)	0.022
Flossing Brushing	-1.028 (0.392)		

There was no significant three-way interaction between intervention, academic year and order of intervention. Therefore, we assessed if there was two-way interaction. There were no significant two-way interaction between intervention and order of intervention, academic year and order of intervention, and intervention and academic year.

There was significant difference of BOP between brushing flossing and flossing brushing (P=0.022). Mean change score (Post – Pre) of BOP in brushing flossing was 0.396 while it was -1.028 in flossing brushing.

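### One null covers plaque and bleeding with no primary outcome, alpha or multiplicity rule, so the BPI claim at P=0.022 is unadjusted; Holm over the two outcomes gives 0.044

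*Protocol*

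**What the plan says.** Protocol section 1.5 gives one null for both outcomes: "The sequence of brushing and flossing doesnot influence plaque control and gingival inflammation". The specific objectives in section 1.3.2 treat plaque and bleeding separately for each sequence in (a) to (d). The only comparative one, (e), names no outcome: "To compare the effectiveness of Brushing first and flossing later versus Flossing first brushing later". The general objective in section 1.3.1 names both.

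Section 4.4 sets the two outcomes side by side: "Dependent Variable: Rustogi Modified Navy Plaque Index (RMNPI) scores and bleeding point index (BPI) Scores". The SAP does the same under Variables and Research Tools, where the dependent variables are "BPI scores and RMNPI scores". Neither document ranks them.

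Protocol section 4.5 covers change scores and descriptive statistics only. The SAP adds ANOVA as its inferential method. Neither states a significance level, says which pattern of results rejects the joint null, or mentions multiplicity.

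The SAP's results tables then test the outcomes one at a time. For BPI (called BOP in that text) it concludes "There was significant difference of BOP between brushing flossing and flossing brushing (P=0.022". For RMNPI it reports no significant difference (P=0.971).

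**The concern.** A single null that covers two outcomes needs a rule saying what rejects it. Without one, and with no primary outcome, a reader cannot tell whether bleeding was the main question or the outcome that happened to differ. The trial had two unadjusted chances to find a difference between sequences, and its one positive claim comes from one of them.

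The protocol's literature table makes this matter more. The two earlier crossover studies of sequence summarised there reported an advantage of flossing first on plaque. Here plaque shows no difference, and the claim rests on bleeding. At stake is how strongly P=0.022 and its interval support that claim.

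**Working it through.** **Inputs from the documents**
- BPI change, SAP Table 2.2: brushing first 0.396, flossing first -1.028; difference 1.424, 95% interval 0.221 to 2.628, P=0.022.
- RMNPI change, SAP Table 3.2: difference -0.058, 95% interval -3.335 to 3.219, P=0.971.
- 30 participants, 15 per order (SAP, Participant Flow Overview).

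**Assumptions, because the documents are silent**
- Two-sided 0.05 per outcome. This fits the 95% intervals and the use of the word significant at P=0.022.
- The joint null is rejected if either test is significant.
- About 26 degrees of freedom: 30 participants less 4 year-by-order cells. The range 22 to 29 is shown where it matters.

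**Step 1: reproduce the reported P values**

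SE = interval width / (2 × t(0.975, df)), then t = difference / SE.

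BPI: 0.396 - (-1.028) = 1.424. SE = (2.628 - 0.221) / (2 × 2.0555) = 0.5855. t = 1.424 / 0.5855 = 2.432, so P = 0.0222. For df 22 to 29, P runs from 0.0225 to 0.0220.

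RMNPI: SE = (3.219 + 3.335) / (2 × 2.0555) = 1.594. t = -0.058 / 1.594 = -0.036, so P = 0.971.

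Both reported P values are reproduced. The BPI P value is the plain one belonging to its 95% interval, so no adjustment for the second outcome is built in.

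**Step 2: chance of falsely rejecting the joint null under the either-outcome rule**

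Independent tests: 1 - 0.95² = 0.0975. For correlated tests, taking the two statistics as bivariate normal:

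| Correlation | Chance of at least one false rejection |
|---|---|
| 0 | 9.75% |
| 0.3 | 9.5% |
| 0.5 | 9.1% |
| 0.8 | 7.8% |
| 0.9 | 7.0% |

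The 9.75% is the maximum for jointly normal two-sided tests. With no assumption on dependence the bound is 0.05 + 0.05 = 10%.

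**Step 3: Holm across the two outcomes**

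The smaller P value is compared with 0.05 / 2 = 0.025, and 0.022 is below it. Adjusted BPI P = 2 × 0.022 = 0.044. The larger P value is then compared with 0.05, and RMNPI stays at 0.971.

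**Step 4: Bonferroni interval for BPI**

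t(0.9875, 26) = 2.379. Half-width = 2.379 × 0.5855 = 1.393. The 97.5% interval is 1.424 ± 1.393, or 0.03 to 2.82. The lower limit rounds to 0.03 for every df from 22 to 29.

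**The case against.** The best counter-argument is that the either-outcome rule is imputed. The SAP never says it rejects the joint null. It draws one conclusion for bleeding and another for plaque, and objectives (a) to (d) already keep the two apart. If these are separate questions, each claim carries its own error rate and 9.75% describes no claim the trial makes. If instead both outcomes had to be significant, the error rate under the joint null would be at most 5% (0.05² = 0.25% if independent), and the reported results would not reject. Part of this stands: the error rate is conditional on a rule nobody wrote down. But section 1.5 does join the outcomes in one null. The conclusion drawn about that null depends on the missing rule, and that is the defect.

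It is also fair to say that both outcomes are reported with estimates, intervals and P values, so nothing is hidden, and that no significance label changes. That stands, and it limits the size of the point.

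A reader might infer that the BPI claim fails once the marginal and interdental areas of RMNPI are counted as further tests. The documents do not support that. Those areas are described in the definition of the index, but no test of them is planned or reported, and the SAP tables give one RMNPI score. A reader might also infer that no primary outcome was ever named. The protocol cites a registration that is not part of these documents, so the statement can cover only the protocol and SAP.

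**Conclusion.** The point holds as an omission of moderate size. The plan states one null over two co-equal outcomes and gives no alpha, rejection rule or multiplicity rule, and the only positive claim is reported unadjusted.

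Under the stated assumptions the false-rejection chance is 9.75% for independent tests and still 7.8% at correlation 0.8, against a nominal 5%. Adjustment doubles the BPI P value from 0.022 to 0.044 and moves the lower limit for the difference from 0.221 to about 0.03. It does not overturn the result: BPI remains below 0.05, by a thin margin. RMNPI is unaffected. To read the omission as showing that the bleeding result is false, or that BPI was chosen after the fact, would go beyond what the documents show.

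**What to change.** In protocol section 1.5 and in the SAP:
- State one null for BPI and one for whole-mouth RMNPI, each comparing brushing first with flossing first.
- Set a two-sided 0.05 familywise level and apply Holm across those two comparisons. Label the rule post hoc, because the results are already known.
- Report adjusted P values (BPI 0.044, RMNPI 0.971) beside the unadjusted ones.
- Give the 97.5% interval for the BPI difference, about 0.03 to 2.82, identified as a Bonferroni interval. Recompute it with the model's actual degrees of freedom.
- Say in the text that the BPI difference is below 0.05 only marginally after adjustment.
- Do not now name BPI the sole primary outcome. With the results known, that choice would remove the adjustment without justification.

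The cost is a few lines of wording, two adjusted P values and one interval, with no new data. The drawback is that the BPI result looks less favourable, at 0.044 instead of 0.022.

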4.1 Study Design

4.1.1 Type of study

Single blind, cross-over randomized clinical trial

4.1.2 Sampling method

Non probability sampling and recruiting volunteers

4.1.3 Randomization

Computer generated randomization sequence (AB/BA)

4.2 Study Period

4.2.1 Reference Population

Dental students studying in MMMC, Melaka

4.2.2 Source Population

Phase II (Year 4 & 5) dental students studying in MMMC, Melaka

4.2.3 Sampling Frame

-Inclusion Criteria: Healthy students of either gender.

-Exclusion Criteria: Probing depth and attachment loss ≥ 3 mm, use of antibiotics in the past 3 months, smoking, active orthodontic treatment, orthodontic retainers.

4.3 Sample Size Calculation

Since there is no previous study available with mean and SD, A pilot study was conducted on 30 participants.

4.4 Variables and Research Tools

Independent Variable: Sequence of brushing and flossing

Dependent Variable: Rustogi Modified Navy Plaque Index (RMNPI) scores and bleeding point index (BPI) Scores

Tools: Head cap, Face mask, Gloves, Mouth mirror, Oral prophylaxis paste, Oral prophylaxis cup/brush, Micromotor, Disclosing agent, William's probe.

Inter examiner reliability

Prior to the start of the study, the examiner was trained by an experienced periodontist until reaching informal agreement on the diagnostic criteria. After that, calibration with 10 participants was performed. Two assessments of the scoring criteria of the index was performed with 1-hour interval. When the strength of the kappa coefficient was 0.78, the data was recorded.

Experimental procedure

Clinical Trial was registered in ClinicalTrials.gov PRS on July 4th 2019 (ID: NCT03989427). Following selection of participants after applying inclusion and exclusion criteria, written informed consent was obtained. Participants received instructions about oral hygiene from DJ. They were subjected to a thorough dental prophylaxis for complete removal of dental plaque from JG. Then, dental plaque was stained with disclosing agent followed by a mouth rinsing with water for 1 min. All erupted teeth, except for third molars, were examined by a blind examiner (SA) at 6 sites per tooth (mesio-buccal, mid-buccal, distobuccal, mesio-lingual, mid-lingual, and distolingual surfaces) for RMNPI score and BPI score.

To ensure standardization, the participants were briefed on the type of toothbrush, toothpaste and dental floss to be used in the study. The amount of dentifrice used was equivalent to half-length of the toothbrush's head. Additionally, the Bass method of brushing and Spool method of flossing was taught to the participants during the baseline appointment. . The methods of toothbrushing and flossing were explained to the participants by a step-by-step video. The participants were instructed to brush for two minutes which corresponds to 1 min for each hemiarch, 30s for buccal surfaces and 30 s for lingual/palatine surfaces.

Cross-over design was used. The participants were studied in two phases with a 1-week wash-out interval. In the first phase of the study, 15 participants were asked to floss first and brush later for two weeks (method FB) and the remaining 15 participants were asked to brush first and floss later for two weeks (method BF). In the second phase, the participants were asked to do the opposite, i.e. floss after brushing, for another two weeks (method BF) and vice versa. In the wash-out period, the participants were asked to use their toothbrush and floss according to their usual routine. Dental prophylaxis was repeated at the beginning of the second phase in order to create the same baseline conditions as at the start of the first phase and study indices were measured again. For measuring RMNPI score, disclosing tablets were given to the participants to chew and rinse. The index score was calculated according to the guidelines.

Bleeding point index were determined at the buccal, lingual and proximal surfaces using the BPI. Periodontal probe was inserted 1 mm into the sulcus at the distal aspect of the tooth and moving it across the length of the sulcus to the mesial on the facial and lingual surfaces. Bleeding surfaces after 20–30 s was recorded. The percentage of the number of bleeding surfaces was calculated.

[figure not shown]
ADA specification of toothbrush: Soft-bristled, No. of bristle are 80-85 per tufts, No. of rows are 2- 4 rows per brush, Length: 25.4-31.8mm. Width: 7.9-9.5mm. Modified bass technique
Dental floss: A thin waxed, fluoridated dental floss used to clean between the teeth³, spool method

Dentifrice: toothpaste containing 1450 ppm fluoride. Brushed for three minutes with their assigned toothbrush with 1.5 g of toothpaste³

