#### **5.3 Inferential Statistic answering the objectives**

## Operational Definitions

### 1. Rustogi Modified Navy Plaque Index(RMNPI):

This index divides buccal and lingual surfaces into nine areas(A to I) that are scored for the presence (score=1) or absence (score=0) of plaque.

Whole mouth=Areas A,B,C,D,E,F,G,H and I; Marginal areas A,B and C; Interdental D and F

Presence of plaque: Score 1

Absence of plaque: Score 0

Buccal surface- 9 areas (A to I)

Lingual surface- 9 areas (A to I)

Interdental - D and F

RMNPI Score=  $(\text{Sum of all "1" marks}) / (\text{Total number of sites score})$

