**Plaque score (RMNPI)**

Table 3.1: Interaction between intervention, academic year and order of intervention on plaque score (RMNPI)

Interaction	P value
Intervention*Academic year*Order of intervention	0.282
Intervention*Academic year	0.050
Intervention*Order of intervention	0.497
Academic year*Order of intervention	0.184

Table 3.2: Plaque (RMNPI) change score (Post – Pre) between two Brushing Flossing and Flossing Brushing

	Mean (SE)	Mean difference (95% CI)	P value
Brushing Flossing	0.042 (1.043)	-0.058 (-3.335, 3.219)	0.971
Flossing Brushing	0.101 (1.427)		

There was no significant three-way interaction between intervention, academic year and order of intervention. Therefore, we assessed if there was two-way interaction. There were no significant two-way interaction between intervention and order of intervention, academic year and order of intervention, and intervention and academic year.

There was no significant difference of plaque score (change from baseline) between brushing flossing and flossing brushing (P=0.971).

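### RMNPI is defined on 18 areas per tooth as a 0-1 ratio, but section 4.4 names six sites for it, and the Table 3.2 standard errors cannot be on the 0-1 scale

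*Protocol*

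**What the plan says.** **Definition.** The Operational Definitions are the same in both documents. The SAP begins: "This index divides buccal and lingual surfaces into nine areas(A to I) that are scored for the presence". Nine areas are listed for the buccal surface and nine for the lingual surface, and the Protocol adds "Whole mouth=Areas A,B,C,D,E,F,G,H and I". The score is the sum of the positive marks divided by "Total number of sites score". There is no factor of 100. BPI, defined next to it, does carry one; its formula is introduced with "The percentage of the number of bleeding surfaces will be calculated by".

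**Procedure.** Protocol section 4.4 (Experimental procedure) says that all erupted teeth except third molars were examined "at 6 sites per tooth (mesio-buccal, mid-buccal, distobuccal, mesio-lingual, mid-lingual, and distolingual surfaces) for RMNPI score and BPI score". Later in the same procedure, the only further statement on how RMNPI was scored is "The index score was calculated according to the guidelines".

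**Result.** SAP Table 3.2 gives the RMNPI change (post minus pre) as 0.042 (SE 1.043) for brushing then flossing and 0.101 (SE 1.427) for flossing then brushing. The difference is -0.058, with 95% CI -3.335 to 3.219 and P=0.971. No unit is given. The text concludes: "There was no significant difference of plaque score (change from baseline) between brushing flossing and flossing brushing".

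**The concern.** There are two separate problems with one of the trial's two dependent variables.

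First, the scoring rules conflict. The definition needs 18 marks per tooth. Section 4.4 names six sites, three buccal and three lingual, and assigns them expressly to RMNPI as well as to BPI. Six marks do not supply 18 area scores.

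Second, the reported results do not match the defined scale. If each score lies between 0 and 1, a change lies between -1 and 1, and standard errors above 1 for a mean over 30 people look impossible.

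What is at stake is the meaning of the null plaque result. Plaque control is part of the general objective and of the null hypothesis. Without a known area set and unit, a reader cannot tell whether the interval excludes a plaque difference that would matter.

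**Working it through.** **Inputs.** 30 participants, 15 per order (Protocol 4.4; SAP Participant Flow Overview). Two academic years (Protocol 4.2.2). Three-way mixed ANOVA with intervention, order and academic year (SAP). The order-by-year layout has four cells, so the error df is 30 - 4 = 26 if nobody is lost. SEs, CI and P come from Table 3.2.

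**Step 1: reproduce the reported figures.**
- CI half-width: (3.219 + 3.335)/2 = 3.277.
- SE of the difference: 3.277/2.0555 = 1.594, where 2.0555 is the 97.5% point of t on 26 df.
- t = 0.058/1.594 = 0.036, giving P=0.971, as reported. The result is the same for the df tried between 20 and 29.
- Implied correlation between the two changes: (1.043² + 1.427² - 1.594²)/(2 × 1.043 × 1.427) = 0.20.
- The two means differ by -0.059 against the stated -0.058, which is rounding.

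Table 3.2 is therefore internally consistent.

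**Step 2: largest possible SE on the defined scale.** The change lies in [-1, 1], so the sum of squares about the mean cannot exceed n.

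- *Simple mean, n=30:* sqrt((30/29)/30) = 0.186.
- *ANOVA marginal mean over four cells:* SE = sqrt(MSE × Σ(1/n_c)/16). The largest within-cell sum of squares is n_c for an even cell and n_c - 1/n_c for an odd one, which is zero for a cell of one person. Over all splits with 15 per order, the maximum is at cells 14, 1, 14, 1. There SS = 28, MSE = 28/26 = 1.077 and Σ(1/n_c) = 2.143, so SE = sqrt(1.077 × 2.143/16) = 0.380.
- *Without the 15/15 constraint:* the maximum is at 27, 1, 1, 1 and equals 0.444.
- *Loose ceiling for any four cells* (every n_c at least 1, SS at most 30): sqrt((30/26) × (4/16)) = 0.537.

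| | SE |
|---|---|
| Simple mean, maximum | 0.186 |
| Worst order-by-year split, 15 per order | 0.380 |
| Loose ceiling, any four cells | 0.537 |
| Table 3.2, brushing then flossing | 1.043 |
| Table 3.2, flossing then brushing | 1.427 |

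**Step 3: can anything rescue the 0-1 reading?**
- *Missing data:* the loose ceiling for n analysed is sqrt((n/(n-4))/4). It is 0.866 at n=6 and 1.118 at n=5, so it stays below 1.043 for any n of 6 or more.
- *SDs mislabelled as SEs:* the largest SD at n=30 is sqrt(30/29) = 1.017, still below both values.
- *The difference itself:* it lies in [-2, 2], so its loose SE ceiling is 2 × 0.537 = 1.074, against 1.594 from the reported CI.

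**Step 4: what the unit decides.** Treated as simple means, the SEs imply SDs of 1.043 × sqrt(30) = 5.7 and 1.427 × sqrt(30) = 7.8 units. On a percentage scale the CI spans about 3.3 points either side of zero. If the score were instead a per-tooth sum out of 18 (an assumption, for illustration only), the same half-width would be 3.277/18 = 18% of the scale. These support very different statements about the absence of a difference.

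**The case against.** The strongest case on the other side has three parts.

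*The six-site sentence may be loose.* It covers both indices at once. It could describe the regions of the tooth inspected, within which areas A to I were then marked, or it could state the bleeding sites carelessly for both. The definitions are explicit, and the procedure says that the guidelines were followed. A figure in section 4.4 that could not be read here might show an area map. This stands in part. A reader might infer that only six sites were scored, and the documents do not support that: they show conflicting wording, not what was done. The conflict remains, because six sites are assigned to RMNPI by name and the reference to guidelines gives no area set, denominator or scale.

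*The scale problem may be no more than a missing factor of 100.* That is quite possible, and a percentage fits the reported SDs. But no text says that RMNPI was analysed as a percentage, and the neighbouring BPI formula does write the factor out, so it cannot be taken as understood.

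*The test result is untouched.* This stands in full. A reader might infer that P=0.971 is wrong or that the comparison is biased. Neither follows. Multiplying by a constant leaves P unchanged, P reproduces from the reported CI, and section 4.4 has one blinded examiner doing the scoring. Nothing shows that scoring differed between the two sequences.

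**Conclusion.** Wrong as written, on two counts that carry different certainty.

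The scale mismatch is certain. The reported SEs are about twice (1.043/0.537 = 1.9) and nearly three times (1.427/0.537 = 2.7) a ceiling that is itself generous. The result needs only the RMNPI formula as written and at least six people analysed across four order-by-year cells. It does not depend on any view of how variable plaque scores are. The documents do not say which scale was used, so the interval of -3.335 to 3.219 has no established unit.

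The conflict between 18 areas and six sites is certain as a matter of wording. Which was done is unknown. If only six sites were scored, the result is not for RMNPI as both documents define it.

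What is affected is the interpretation of the plaque result, not its significance test.

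**What to change.** 1. Check the scoring records for the areas marked per tooth, the denominator and the scale entered for analysis.
2. Reconcile the Operational Definitions (Protocol and SAP) with the procedure in Protocol section 4.4, so that RMNPI has one area set, one denominator and one scale. Replace the bare reference to guidelines with that rule.
3. State the unit in Table 3.2. If it is a percentage, add the factor of 100 to the RMNPI formula in both documents.
4. If only six sites were scored, say so, and do not report the score as RMNPI as defined.
5. Word the plaque conclusion in the SAP for the score and unit actually analysed, and give its 95% CI beside the P value.

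The cost is a records check and wording corrections. No new data are needed, and no re-analysis unless the records show a scoring or scaling error.
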